5.2.2.1. Analysis of pregnancy related events of interest planned in the protocol

The number and percentage (with exact 95% CI) of pregnant women presenting with the following events of interest will be tabulated for each event within appropriate time windows. Missing data may be considered a separate category.

5.2.2.2. Additional Considerations:

This analysis will be done on the maternal PPS. For events of interest that include subcategories, the frequency of the main event of interest and of each event subcategory will be included in the analysis. The overall frequency (derived programmatically) will include mothers who present with at least one of the subcategory events. The intervals of interest are Visit 1 up to 42 days after Visit 5. All events reported during the entire study period will be included in this analysis.

Details of exact confidence intervals analysis are described in section [9.5.2](#).

All frequencies will be reported overall, by country, and if applicable, by region. Frequencies of pregnancy related events of interest will also be presented by age strata (18-34, 35-39, ≥ 40 years). The number and percentage of the following events will be reported:

- Maternal death
- Hypertensive disorders of pregnancy:
 - Gestational hypertension,
 - Pre-eclampsia,
 - Pre-eclampsia with severe features (including eclampsia)
- Antenatal bleeding:
 - Morbidly adherent placenta

- Placental abruption
- Cesarean Scar Pregnancy
- Uterine rupture
- Postpartum hemorrhage
- Fetal growth restriction
- Dysfunctional labor
 - first stage of labor
 - second stage of labor
- Gestational diabetes mellitus,
- Non reassuring fetal status
- Pathways to preterm birth:
 - Premature preterm rupture of membranes,
 - Preterm labor,
 - Provider-initiated preterm birth.
- Chorioamnionitis
- Oligohydramnios
- Polyhydramnios
- Gestational Liver Disease:
 - Intrahepatic Cholestasis of Pregnancy (ICP)
 - Acute Fatty Liver of Pregnancy
- Maternal Sepsis
- Any other pregnancy related event considered by the investigator to be of concern

5.2.3. To determine the frequencies of neonatal events of interest in all neonates live-born to women enrolled in the study.

5.2.3.1. Analysis of neonatal related events of interest planned in the protocol

The number and percentage (with exact 95% CI) of neonates presenting the following events of interest will be tabulated for each event. Missing data may be considered a separate category.

5.2.3.2. Additional Considerations

This analysis will be done on the infant PPS, overall, by country, and if applicable, by region.

For events of interest that include subcategories, the frequency of the main event of interest and of each event subcategory will be included in the analysis. The overall frequency will include infants who present at least one of the subcategory events.

Details of exact confidence intervals analysis are described in section [9.5.2](#).

The number and percentage of the following events will be reported:

- Small for gestational age,
- Low birth weight including very low birth weight,
- Neonatal encephalopathy,
- Congenital microcephaly,
 - Postnatally diagnosed
 - Prenatally diagnosed
- Congenital anomalies,
 - Major external structural defects
 - Internal structural defects
 - Functional defects
- Neonatal death,
 - Neonatal death in a preterm live birth (gestational age \geq 28 to < 37 weeks)
 - Neonatal death in a term live birth
- Neonatal infections,
 - Blood stream infections
 - Meningitis
 - Respiratory infection
- Respiratory distress in the neonate,
- Preterm birth,
- Failure to thrive,
- Large for gestational age,
- Macrosomia,
- Any other neonatal event considered by the investigator to be of concern (specify, e.g. neurodevelopment delay)

5.3. Analysis of secondary objectives

The secondary objectives analyses will be performed on the PPSs (maternal or infant as applicable) overall and possibly by region or other relevant grouping. *If there is difference of 5% or more between the number of participants in the enrolled set and the PPS, tertiary objectives analyses on the enrolled set will also be performed.*

5.3.1. To determine frequencies of fetal death/still birth according to GAIA levels of diagnostic certainty.

5.3.1.1. Analysis planned in the protocol

N/A

5.3.1.2. Additional considerations

This objective will not be performed.

5.3.2. To determine frequencies of pregnancy related events of interest according to GAIA levels of diagnostic certainty (where these are specified) in healthy pregnant women with uncomplicated pregnancies at time of enrolment.

5.3.2.1. Analysis of pregnancy related events of interest planned in the protocol.

To determine the frequencies of pregnancy related events of interest according to GAIA levels of diagnostic certainty (where these are specific) (APPENDIX D of protocol).

Considering all pregnant women followed from enrolment through Visit 6, the number and percentage of subjects with at least one maternal event of interest will be computed by GAIA levels of diagnostic certainty, with exact 95% CIs.

5.3.2.2. Additional considerations

This analysis will be done on the maternal PPS, overall and by country. If the frequencies of categories of events of interest are low, the results will also be presented by region.

Details of exact confidence intervals analysis are described in section 9.5.2.

Among the pregnancy related events of interest from Section 3.1.2.2, those with GAIA levels of diagnostic certainty will be presented in this analysis. For each event, the frequency of mothers with a specific diagnostic level of certainty will be reported. For events with subcategories, main events will not be presented since the levels of diagnostic certainty do not apply to the main categories because GAIA levels do not exist for the main categories.

Please note that GAIA levels are explained in detail in the Appendix D of the study protocol.

5.3.3. To describe the distribution of RSV-A antibody titres in maternal blood at delivery in healthy pregnant women with uncomplicated pregnancies at time of enrolment.

5.3.3.1. Analysis of RSV-A antibody titres in maternal blood collected at delivery planned in the protocol

To describe the distribution of RSV-A antibody titres in maternal blood at delivery.

- Geometric mean titres (GMTs) will be tabulated with 95% CI.
- Percentage of subjects above thresholds will be tabulated.

5.3.3.2. Additional considerations

This analysis will be done on the maternal PPS, overall and by country.

RSV-A neutralising antibodies will be obtained from maternal and cord blood collected at delivery. The frequency and percentage of subjects with titres above the threshold will be presented along with 95% CI. GMTs and corresponding 95% CI, minimum and maximum values will be reported.

5.3.4. To determine frequencies of neonatal events of interest according to GAIA levels of diagnostic certainty (where these are specified) in all neonates live-born to women enrolled in the study:

5.3.4.1. Analysis of neonatal events of interest planned in the protocol

To determine frequencies of neonatal events of interest according to GAIA levels of diagnostic certainty (where these are specified) (APPENDIX D of protocol). Neonatal events of interest occur within the first 28 days after birth, but may only be detected later and are to be reported throughout the study.

Considering all neonates the number and percentage of subjects with at least one neonatal event of interest will be computed by GAIA levels of diagnostic certainty, with exact 95% CI.

5.3.4.2. Additional considerations:

This analysis will be done on the infant PPS overall and by country. Among the neonatal events of interest identified in section 3.1.2.3, those with GAIA levels of diagnostic certainty will be presented in this analysis. For each event, the frequency of infants with a specific diagnostic level of certainty will be reported. For events with subcategories, main events will not be presented because GAIA levels do not exist for the main categories.

Please note that GAIA levels are explained in detail in Appendix D of the study protocol.

5.3.5. To describe the distribution of RSV-A antibody titres in cord blood at delivery in all neonates live-born to women enrolled in the study:**5.3.5.1. Analysis of RSV A antibody titres in cord blood planned in protocol**

To describe the distribution of RSV-A antibody titres in cord blood at delivery

- Geometric mean titres (GMTs) will be tabulated with 95% CI.
- Percentage of subjects above thresholds will be tabulated.

5.3.5.2. Additional considerations:

A correction/elaboration from the analysis planned in protocol in section 5.3.5.1 is that we will be reporting on the percentage of subjects with GMTs above thresholds.

This analysis will be done on the Infant PPS, overall and by country.

RSV-A neutralising antibodies will be measured in the cord blood at delivery. The frequency and percentage of subjects with titres above the threshold will be presented along with 95% CI. GMTs and corresponding 95% CI, minimum and maximum values will be reported.

5.3.6. To determine the incidence of all, of severe, and of very severe RSV-lower respiratory tract illnesses (LRTIs) in all neonates/infants live-born to women enrolled in the study:**5.3.6.1. Analysis of RSV LRTI in all neonates/infants planned in protocol**

Considering all infants followed from visit 1-NB to visit 4-NB, the percentage of subjects with at least one LRTI illness, exact 95% CI will be presented.

Incidence rates of LRTI illnesses will be calculated, with exact 95% CI.

Frequencies of repeat occurrences of LRTI will be tabulated.

5.3.6.2. Additional considerations

A correction from the analysis planned in protocol in section 5.3.6.1 is that we will be reporting on all cause LRTIs and RSV associated LRTIs.

This analysis will be based on the infant PPS and will be done on the first episode of all, of severe, and of very severe RSV LRTIs (Section 2.2).

Incidence analyses will be performed overall, by country and by age strata (0-2 months, 0-5 months, and 0-11 months). If applicable (in the case of low numbers of incidence), incidence analyses will also be presented by region (Section 9.3). Incidence rates will also be calculated in one-month intervals from birth to one year of age, please see the monthly infant age intervals in Section 9.3.

The analysis of RSV disease incidence is summarized in the table below showing endpoints and analytic methods, these include incidence rate, proportion affected, and incidence proportion.

Incidence rate is the number of first events per person time. Incidence proportion is the number of first RSV LRTI over population at risk during the specified time period (0-2 months, 0-5 months and 0-11 months). Proportion affected is the number of subjects with at least one episode of RSV LRTI at age interval over the total number of subjects at the start of the age interval.

For each of the RSV LRTI endpoints listed in [Table 11](#), the 95% CI will be computed as described in section [9.5.2](#). Kaplan-Meier curves presenting the cumulative probability of the first episode will be displayed overall. The cumulative probability of presenting the first episode will be given with its 95% CI at the end of the follow-up.

Frequencies of repeat occurrences of RSV LRTI, severe LRTI and very severe LRTI will be tabulated.

Cumulative incidence will be presented from birth to one year of life by monthly intervals (Subgroups in section [9.3](#)).

Table 6 Summary of RSV incidence analyses for RSV LRTI of infants from birth to 1 year (Visit 1-NB to visit 4-NB)

Endpoints	Incidence analysis method	Subgroup
All RSV LRTI Severe RSV LRTI Very Severe RSV LRTI	Incidence rates of first episode Cumulative probability of first episode (Kaplan Meier)	Overall, by country, and by age strata
All RSV LRTI Severe RSV LRTI Very Severe RSV LRTI	Proportion affected by all new episodes	Overall, by country, and by age strata
All RSV LRTI Severe RSV LRTI Very Severe RSV LRTI	Incidence proportion of first episode	Overall and by country within each age strata)

5.3.7. To determine the incidence of RSV hospitalization in all neonates/infants live-born to women enrolled in the study:

5.3.7.1. Analysis of RSV hospitalization planned in protocol

Considering all infants followed from visit 1-NB to visit 4-NB, the percentage of subjects with at least one RSV hospitalization, with exact 95% CI.

Incidence rates of RSV hospitalizations will be calculated, with exact 95% CI.

Frequencies of repeat occurrences of RSV hospitalization will be tabulated.

5.3.7.2. Additional considerations

This analysis will be performed on the infant PPS and the first episode of RSV hospitalization, overall and by country and by age strata. In addition to incidences of RSV hospitalization, we will also consider all cause LRTI hospitalizations.

A change from the planned analysis in section 5.3.7.1 is that only the first event of RSV hospitalization will be included in the analysis.

In addition, cumulative incidence, Kaplan-Meier curves, and proportion affected will be calculated.

Lastly, we will also present the frequencies of symptoms used in case definitions among those infants who are found to be RSV positive from nasal swab results. The symptoms that will be considered are:

- Runny nose
- Blocked nose
- Cough
- Wheezing
- Grunting
- Nasal flaring
- Intercostal recession
- Temperature ≥ 38 degrees Celsius
- Chest wall indrawing
- SpO₂ cutoff point for hypoxemia

5.4. Analysis of tertiary objectives

The following tertiary objectives analyses will be performed on infants within the PPS overall and possibly by region or other relevant grouping. *If there is difference of 5% or more between the number of participants in the enrolled set and the PPS, tertiary objectives analyses on the enrolled set will also be performed.*

5.4.1. To describe co-infections of RSV-LRTI with other respiratory viruses in infants.

5.4.1.1. Analysis of respiratory viruses associated with RSV-LRTI as planned in protocol

Considering all infants followed from visit 1-NB to visit 4-NB, the percentage of subjects with the occurrence of RSV-LRTI and having other respiratory viral co- infection with another viral etiology identified by multiplex PCR, with exact 95% CI; classified by respiratory viruses.

5.4.1.2. Additional considerations

This analysis will be performed on the Infant PPS.

The number and percentage of cases for each respiratory virus will be identified for all RSV LRTI, severe RSV LRTI, and very severe RSV LRTI. For each respiratory virus infection, number and percentage will be summarized by single or co-infection status. The groups will include those who are:

*RSV positive (confirmed with nasal swabs)

*RSV positive (confirmed with nasal swabs) & positive with another infection

*RSV negative (confirmed with nasal swabs) & positive with another infection.

For cases of RSV LRTI, severe RSV LRTI and very severe RSV LRTI, the number and percentage of cases associated with at least one other respiratory virus will be described.

This analysis will be performed overall, by country, and by age strata (0-2 months, 0-5 months, and 0-11 months).

Other respiratory viruses causing infection:

- Influenza A virus (Flu A)
- Influenza B virus (Flu B)
- Human Influenza A virus subtype H1 (Flu A-H1)
- Human Influenza A virus subtype H3 (Flu A-H3)
- Human Influenza A virus subtype H1pdm09 (Flu A-H1pdm09)
- Human adenovirus (AdV)
- Human metapneumovirus (MPV)
- Human enterovirus (HEV)
- Human parainfluenza virus 1 (PIV1)
- Human parainfluenza virus 2 (PIV2)
- Human parainfluenza virus 3 (PIV3)
- Human parainfluenza virus 4 (PIV4)
- Human bocavirus 1/2/3/4 (HBoV)
- Human rhinovirus A/B/C (HRV)
- Human coronavirus 229E (229E)
- Human coronavirus NL63 (NL63)
- Human coronavirus OC43 (OC43)

Lastly, an additional analysis will be performed that considers the frequencies of clinical symptoms of two groups of infants: those who have RSV LRTI and those who have LRTI but are RSV negative.

The clinical symptoms that will be considered are:

- Runny nose
- Blocked nose
- Cough
- Wheezing
- Grunting
- Nasal flaring
- Intercostal recession
- Temperature ≥ 38 degrees Celsius
- Chest wall indrawing
- SpO₂ cutoff point for hypoxemia

5.4.2. To estimate the association of RSV-LRTI in neonates/infants and the level of RSV neutralizing antibodies in cord blood.

5.4.2.1. Analysis of association of RSV-LRTI in neonates and level of RSV neutralizing antibodies in cord blood as described in the protocol.

Correlation analysis will be done comparing the levels of RSV antibodies present in cord blood and the presence or absence of RSV-associated LRTI, RSV-associated severe LRTI, and RSV-associated very severe LRTI in infants.

5.4.2.2. Additional consideration.

When considering RSV antibodies in cord blood, we are only considering RSV-A antibodies at this time (however, in the future we might also consider RSV-B antibodies). When considering RSV positivity status in nasal swabs, we consider positivity for RSV-A or RSV-B.

This analysis will be performed on the Infant PPS and will be done on the first episode (not recurrent events) of RSV LRTIs occurring during the following age intervals: 0-2 months and 0-5 months.

Step 1: Descriptive analysis:

Descriptive analyses (seropositivity rate with 95% CIs, geometric mean, median, min, max) of RSV-A neutralizing antibodies in the baseline cord blood samples will be analysed in only those with RSV positive nasal swab samples.

Next, descriptive analyses (seropositivity rate with 95% CIs, geometric mean, median, min, max) of RSV-A neutralizing antibodies in the baseline cord blood samples will be presented by RSV LRTI, RSV severe LRTI, and RSV very severe LRTI case statuses.

In addition, if further exploration is desired, we may plot levels of RSV A vs RSV-B neutralizing antibodies in cord blood among RSV LRTI positive and negative infants to see if any patterns are observed.

Step 2: Cox models:

The impact of the level of RSV neutralizing antibodies in the baseline cord blood samples on the incidence of first event of RSV-LRTI, RSV-severe LRTI and RSV very severe LRTI separately will be assessed through Cox models.

Cox regression models will be performed for the univariate analyses to obtain unadjusted hazards ratios of the determinants of interest.

Next a multivariable Cox regression model will be performed to estimate the relative contribution of each potential risk factor adjusting for the simultaneous effects of the other covariates. The model will include: time-independent covariates (e.g. gender, etc.) and time-dependent covariates (age). Covariate selection will be done using backward elimination and statistical significance. Potential risk factors will be included in the multivariable models if univariate p-value will be less than 0.1 and the multivariable model will be performed only if the number of events is sufficient (at least 10 events per covariate). In addition, depending on the data, other models could be explored or the model could be simplified.

The following covariates in infants may be considered in the multivariable models:

- Age (continuous)
- Male sex (M/F)
- Small for gestational age (Continuous)
- Congenital anomalies with internal structural defects and/or with functional defects (Y/N)
- Household composition (number of people living in household) (continuous)
- How many children under age of 6 live in household (continuous)
- Cigarette smoking during pregnancy (Y/N)
- Born during RSV transmission season (Y/N)
- Alcohol consumption during this pregnancy (Y/N)
- Highest education level of mother (Y/N)

Step 2-a: RSV neutralizing antibodies classified as a binary variable: Seropositive and seronegative:

In a first step, the RSV-A neutralizing antibodies in the baseline cord blood samples will be introduced in the model as binary variable

Step 2-b: RSV neutralizing antibodies classified as semi-quantitative variable: Quartiles

In a second step, the RSV-A neutralizing antibodies levels in baseline cord blood will be introduced in the model using quartiles. And the Cox models will be performed as described in the previous paragraph (RSV-A neutralizing antibodies as quantitative variable).

Step 2-c: RSV neutralizing antibodies classified as continuous variable:

In a third step, the RSV neutralizing antibodies levels in baseline cord blood might be treated as continuous variable in Cox models to evaluate how each unit of neutralizing antibody level change impacts on the above clinical outcomes. The Cox models will be performed as described in the previous section (with log of RSV neutralizing antibodies as quantitative variable). For the subjects with antibody levels below the LOD, a value of LOD/2 will be imputed.

The model with the best fit using, log likelihood criteria, will be selected. This will be determined via backward elimination using statistical significance.

Note that depending on the results, a quantitative association between RSV-associated LRTI, RSV-associated severe LRTI, RSV very severe LRTI, and RSV neutralizing antibodies in the baseline cord blood samples could be further explored and described more in details in the main analysis.

Poisson regression models:

Multivariable Poisson regression of neutralizing RSV A cord blood antibodies estimating RSV LRTI incidence in the first year of life, controlling for covariates will be explored. The same risk factors as above will be test. Modelling will be done in a stepwise manner using backward elimination and statistical significance.

5.4.3. *To determine the incidence of LRTIs/Severe LRTIs (using alternative case definitions)***5.4.3.1. Additional considerations**

Repeat incidence analyses described in section 5.3.6 with alternative LRTIs/Severe LRTIs case definitions.

5.4.4. To determine risk factors for pregnancy related and neonatal events of interest.**5.4.4.1. Analysis of risk factors for pregnancy related and neonatal events of interest as described in the protocol.**

- Both pregnancy related events of interest and neonatal events of interest will be described according to variables collected in the mother's clinical examination and obstetric risk factors. Frequency tables will be generated for categorical variables.
- Furthermore, multiple variable analyses (such as multiple logistic regression for binary outcomes and multiple Poisson/negative binomial and/or other appropriate models for count outcomes) will be conducted to adjust for covariates of interest, provided there are sufficient numbers of events of interest.

5.4.4.2. Additional considerations:

This analysis will be performed on the maternal and infant PPSs depending on whether the risk factors are for pregnancy-related events of interest or for neonatal events of interest.

There are currently 14 potential pregnancy related events of interest and 9 potential risk factors. Likewise, there are 12 potential neonatal events of interest and 13 potential risk factors. (These do not include GAIA subcategories).

Univariate modelling will be done to first determine which risk factors are associated with which event of interest.

For each potential risk factor,

- Frequency tables will be generated as appropriate, for categorical variables.
- Mean, median, standard error, minimum, maximum and number of missing values will be provided as appropriate, for continuous data.

For pairwise distributions

- Cross-tabulations (i.e. two-way frequency tables) will be generated as appropriate, for categorical-categorical pairs;
- Mean, median, standard error, minimum, maximum and number of missing values by category will be provided as appropriate, for continuous-categorical pairs;

Covariates with univariate p-value less than 0.1 will be included in the multivariable model. The number of covariates included in the model will depend on the number of events (at least 10 events per covariates).

Multiple logistic regression, multiple Poisson regression/negative binomial modelling will be used when appropriate only on risk factors and events of interest that were associated in the univariate analysis and provided there are sufficient numbers of events of interest.

5.4.4. If deemed necessary, to further characterize the immune responses to RSV and other infections in maternal subjects and infants (based on maternal serum and cord blood).

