3.3. Tertiary

3.3.1. Tertiary objectives

- To describe co-infections of RSV-LRTI with other respiratory viruses in infants.
- To estimate the association of RSV-LRTI in neonates/infants and the level of RSV neutralizing antibodies in cord blood.
- ***To determine the incidence of LRTIs/ Severe LRTIs (using alternative case definitions)***
- To determine risk factors for pregnancy-related and neonatal events of interest
- If deemed necessary, to further characterize the immune responses to RSV and other infections in maternal subjects and infants (based on maternal serum and cord blood).

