9.3. Subgroup definitions

The following sub-group names will be used for statistical analyses:

Sub-group order in tables	Sub-group label in tables	Sub-group definition for footnote
Country		
1	TH	Subjects from Thailand
2	MY	Subjects from Malaysia
3	PH	Subjects from Philippines
4	SA	Subjects from South Africa
5	BD	Subjects from Bangladesh
6	PA	Subjects from Panama
7	BR	Subjects from Brazil
8	AR	Subjects from Argentina
9	CO	Subjects from Colombia
10	MX	Subjects from Mexico
Region		
Latin America	LatAM	Subjects from Brazil, Argentina, Colombia, Mexico, Panama
Asia Pacific	AsiaPac	Subjects from Thailand, Malaysia, Philippines, Bangladesh
South Africa	SA	Subjects from South Africa
Age category maternal subject at enrolment		
1	18-34	18-34 years of age
2	≥35	35 years of age or older
Age category infant (3 categories)		
1	0-2	Birth to one day before the 3rd month of life (0-30 days)
2	0-5	Birth to one day before the 6th month of life (0-180 days)
3	0-11	Birth one day before the 12th month of life (0-365 days)
Age category infant (One-month intervals)		
1	0	Birth to one day before the 1 st month of life
2	1	First day of 1 month to one day before the 2 nd month of life
3	2	First day of 2 months to one day before the 3 rd month of life
4	3	First day of 3 months to one day before the 4 th month of life
5	4	First day of 4 months to one day before the 5 th month of life

Sub-group order in tables	Sub-group label in tables	Sub-group definition for footnote
6	5	First day of 5 months to one day before the 6 th month of life
7	6	First day of 6 months to one day before the 7 th month of life
8	7	First day of 7 months to one day before the 8 th month of life
9	8	First day of 8 months to one day before the 9 th month of life
10	9	First day of 9 months to one day before the 10 th month of life
11	10	First day of 10 months to one day before the 11 th month of life
12	11	First day of 11 months to one day before the 12 th month of life

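### Section 5.4.2.2 sets the cord-blood antibody question at 0-2 and 0-5 months, but its Poisson model runs over the first year with one antibody effect; the windows should be reconciled or the effect allowed to vary by age (minor).

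*SAP*

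**What the plan says.** The tertiary objective in SAP section 3.3.1 is "To estimate the association of RSV-LRTI in neonates/infants and the level of RSV neutralizing antibodies in cord blood". Section 5.4.2.2 opens by stating that the analysis uses the infant per-protocol set and first episodes only, for "RSV LRTIs occurring during the following age intervals: 0-2 months and 0-5 months". The descriptive step and the Cox models follow, with antibody entered as seropositive or seronegative, then in quartiles, then possibly as a continuous log titre.

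The section closes with a separate paragraph on a "Multivariable Poisson regression of neutralizing RSV A cord blood antibodies", with the aim of "estimating RSV LRTI incidence in the first year of life, controlling for covariates will be explored". On covariates it says "The same risk factors as above will be test", with backward elimination by statistical significance. The covariate list includes age, but no antibody-by-age term.

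Section 8 (Changes from planned analyses) does not mention the change of window, and section 9.5.6 only names the software procedure. The 2019 SAP and its Amendment 1, bound in the same file, have the same two windows.

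**The concern.** Two paragraphs under one heading and one objective set different age windows for the same exposure. The omission of 0-11 months from the opening looks like a choice: sections 5.3.6.2 and 5.4.1.2 use three strata (0-2, 0-5 and 0-11 months), and only the antibody section drops the third. The Poisson paragraph brings it back without comment, so a programmer cannot tell whether the restriction applies to it.

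The window matters because the exposure is a single titre fixed at birth. As written, the Poisson model returns one antibody ratio for all 12 months. Age as a covariate adjusts the background rate; it does not let the antibody ratio differ between month 1 and month 11. If the effect is mainly early, the first-year ratio will be nearer to 1 than the Cox hazard ratios at 0-2 and 0-5 months. A reader could then take a difference in follow-up window for a conflict between methods. The study is meant to inform trials of maternal RSV immunization, so that misreading is worth preventing.

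**Working it through.** The SAP states no effect size, event count or power for this model, so there is no figure of its own to reproduce. The check is the share of the year at issue, followed by an illustration.

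**1. Share of follow-up outside the early window.** Section 9.3 footnotes the 0-5 month band as days 0-180 and the 0-11 month band as days 0-365. (365 − 180)/365 = 185/365 = 50.7%.

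**2. First-year ratio with an early effect only.** Assumptions, none from the SAP: the rate ratio is r at 0-5 months and 1 afterwards, and a share e of reference-group events falls at 0-5 months. Ignoring the small change in person-time after first events, the first-year ratio is e × r + (1 − e).

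| e | Early ratio 0.50 | Log ratio kept | Early ratio 0.70 | Log ratio kept |
|---|---|---|---|---|
| 40% | 0.4 × 0.50 + 0.6 = 0.80 | 32% | 0.4 × 0.70 + 0.6 = 0.88 | 36% |
| 50% | 0.75 | 42% | 0.85 | 46% |
| 60% | 0.70 | 51% | 0.82 | 56% |

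Log ratio kept is ln(first-year ratio)/ln(r); for example, ln(0.75)/ln(0.50) = 0.288/0.693 = 42%.

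**3. Effect on power, under the same assumptions.** Schoenfeld's formula with a 50:50 antibody split and two-sided 5% needs 66 early events for 80% power at a ratio of 0.50. With e = 40%, the full year has about 198 events at a ratio of 0.80 and power of about 35%. With e = 50%, it has about 154 events at 0.75 and power of about 43%. For an early ratio of 0.70 (247 early events), the corresponding powers are about 39% and 47%. The extra events do not make up for the smaller effect.

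**4. Gradual waning instead of a cut-off.** Assume a log hazard ratio of ln(0.50) at birth that halves every h days, and a flat background hazard. For h = 30, the average ratio is 0.861 over 0-180 days and 0.930 over 365 days. For h = 80, it is 0.712 and 0.823. Across h = 30 to 80, the first-year log ratio is 48-57% of the 0-5 month value.

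**5. A case with no dilution.** Suppose log hazard is linear in the log of current titre and all infants share one half-life. Two infants whose birth titres differ fourfold then keep that fourfold difference all year. A hazard ratio of 0.50 at birth is still 0.50 at days 180 and 364, and the first-year and 0-5 month ratios agree.

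**The case against.** The longer window may be intended. The Poisson paragraph names its own period and stands apart from the descriptive and Cox steps. A one-year horizon is also normal in this SAP: section 3.2.2 sets the RSV-LRTI endpoint from birth to 1 year. A specific sentence can qualify a general opening. This stands to the extent that the text does not show the first-year window to be a mistake; it shows that the difference is unexplained.

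A reader might infer that the first-year ratio is biased toward no effect. The documents do not support that. It is an average over a longer period, hence a different estimand from the 0-5 month ratio. Whether the two differ depends on waning, on which the SAP is silent, and step 5 gives a plausible case where they do not.

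A reader might also infer that backward elimination would remove a weakened antibody term. That is uncertain. Antibody is the named exposure and is not on the covariate list to which the elimination refers, although the wording does not protect it explicitly.

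Nor would an early association go unseen, because the Cox models fall under the 0-2 and 0-5 month restriction and estimate it directly. Section 9.5.5.2 also leaves room for other models, section 6 asks for cautious descriptive reading, and the Poisson model is only to be explored. These points lower the weight of the concern. They do not remove the mismatch of windows or supply an age-varying effect.

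**Conclusion.** The mismatch is real and can be read directly from section 5.4.2.2: two early windows at the start, a full year at the end, no reason given and no antibody-by-age term. About 51% of the first-year window lies outside the range set at the opening.

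Any shift of the ratio toward 1 is conditional on protection fading with maternal antibody. Its size depends on assumed inputs: with no effect after 6 months and 40-60% of reference-group events at 0-5 months, 0.50 would appear as 0.80 to 0.70. These figures show what could happen, not what the study will find. The practical risk is an apparent disagreement between Poisson and Cox results that only reflects different windows. No primary or secondary result is affected, so the severity is minor.

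**What to change.** Reconcile the two paragraphs of section 5.4.2.2 in one of two ways.

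- Run the Poisson model on first RSV-LRTI at 0-2 and 0-5 months, as in the rest of the section. This costs one sentence and gives up the later events; the result will largely parallel the Cox models.
- Keep the first-year model, label it supplementary to the Cox models, split person-time at 3 and 6 months, and include an antibody-by-age-period interaction. State that antibody stays in the model whatever the elimination step does to the covariates. Report separate ratios for 0-2, 3-5 and 6-11 months.

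The second option loses no events and examines directly whether the association changes with age. Its cost is a little extra programming and less precise period-specific ratios.

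Under either option, first correct the 0-2 month band in section 9.3: its footnote describes the period up to the day before the third month but gives days 0-30.
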